6.3.3 Patient-Reported Outcomes Additional Instructions

All questionnaires will be administered as a paper survey, with the aim that the patient completes questionnaires at the time of scheduled study clinic visits.

The patient should be instructed to respond to the questionnaires in terms of his or her experience during the timeframe specified on each questionnaire.

The patient should be asked to read the instructions at the beginning of each questionnaire and complete all the items. It is permissible to assist the patient with the questionnaires as long as the staff person does not influence the patient's responses.

The questionnaires must be reviewed by the protocol nurse or research coordinator as soon as the patient completes them to ensure all items were marked appropriately. If more than one answer was marked, the patient should be asked to choose the answer which best reflects how he or she is feeling. If a question was not answered, the patient should be asked if he or she would like to answer it. The patient should always have the option to refuse. If the patient cannot complete a questionnaire, or if the patient refuses to complete a questionnaire, the reason should be noted according to the instructions in the EAA171 Forms Completion Guidelines.

If appointments on the scheduled date are missed, the questionnaires will be mailed electronically to participants who will be asked to complete the questionnaires and return answers by electronic mail to the clinic. After 7 days, clinic or research staff may contact participants by telephone and ask participants to complete the questionnaire over the telephone reading their answers to the staff person. This approach will approximate the completion of PROs in clinic as closely as possible.

Rev. Add3

NOTE: When delivering questionnaires to patients by electronic mail or over the telephone, please document the process of distribution and completion carefully and thoroughly in the medical record in case of an audit review.

PRO-CTCAE items will be administered sometimes coincident with other study PRO measures following procedures for PRO administration as described above. PRO-CTCAE items will be administered prior to clinic visits, or prior to participant's discussion of disease status and treatment side effects with health-care professionals. This is modeled after NCI PRO-CTCAE study procedures employed in other clinical trial validation studies. Clinicians will be instructed to complete clinician-rated treatment toxicities (CTCAE) prior to reviewing PRO-CTCAE ratings. This will minimize the extent to which PRO-CTCAE responses introduce a bias to clinician CTCAE ratings. PRO-CTCAE are currently undergoing validation and thus exploratory in nature, therefore, at this point should not be used to inform clinician CTCAE ratings. Clinicians will be instructed to review PRO-CTCAE items after clinician toxicity ratings have been completed to identify any patient-reported symptoms and toxicities that warrant clinical attention. Supportive care measures to manage treatment toxicities are described in Section [5.6](#).

7. Study Parameters

Rev. Add3

7.1 Therapeutic Parameters (for both arms of the study)

1. Pre-study scans and x-rays used to assess all measurable or non-measurable sites of disease must be done \leq 4 weeks prior to randomization.
2. Pre-study CBC (with differential and platelet count) must be done \leq 14 days prior to randomization.
3. All required pre-study chemistries, as outlined in Section 3, must be done \leq 14 days prior to randomization – unless specifically required on Day 1 as per protocol.

Schedule of events

Biological Specimen Submission: MANDATORY for Minimal Residual Disease Assessment		
	Following Pre-Registration	Submit to:
Bone Marrow Aspirate (1) 6mL ACD (yellow top) tube¹⁰	X	Mayo Clinic

Rev. Add3

Study Parameters	Tests and Procedures	Prior to randomization (\leq 28 days unless otherwise noted)	At the end of each cycle	Annually	At study discontinuation or progression (whichever comes first)	28 days after discontinuation of treatment	Post Treatment to 10 years from study entry ⁹
History and Exam, Performance Status, Height ¹⁶ and Weight		X	X		X		
CBC with Differential ¹		X	X		X		
Chemistry Labs ²		X	X		X		
Beta-2 Microglobulin		X					
LDH		X					
SPEP ³		X	X		X		X
Serum M-protein Immunofixation		X ¹³	X ⁷				X ⁷

Study Parameters		At the end of each cycle				Annually		At study discontinuation or progression (whichever comes first)		28 days after discontinuation of treatment		Post Treatment to 10 years from study entry ⁹	
Tests and Procedures	Prior to randomization (≤ 28 days unless otherwise noted)												
24 hr UPEP ³	X	X				X					X		
24 hr Urine M-protein Immunofixation	X ¹³	X ⁷									X ⁷		
Serum Free Light Chain Assay	X	X ⁷				X					X ¹⁵		
Serum Immunoglobulin G, A, M	X	X				X					X		
Bone Marrow Aspirate and/or Biopsy	X			X ¹¹									
¹⁸ F-FDG PET/CT	X ⁸	X ¹²											
Serum or Urine Pregnancy Test ⁴	X	X				X			X				
Adverse Event Assessment	X	X							X				
PRO Assessment ⁵													
MRD													
Registration to Revlimid REMS ^{®14}	X												
Patient Medication Calendar ⁶													

See Section [6.3.2](#)
See above: Biological Specimen Submission table

1. Baseline CBCs (with differential and platelet count) which includes WBC, ANC, Platelets, and Hgb must be done ≤ 14 days prior to randomization. CBCs required for protocol therapy must be done < 4 days prior to the treatment cycle.
2. Chemistry includes sodium, potassium, calcium, blood urea nitrogen (BUN), creatinine, creatinine clearance, glucose, alkaline phosphatase, total bilirubin, aspartate aminotransferase (AST), and alanine aminotransferase (ALT). Magnesium and phosphorus are not required but should be tested as clinically indicated.
3. Assessment is required if used to assess disease response. To confirm V/GPR or higher response, both serum and urine M-components must be evaluated.
4. Patients of childbearing potential must have a negative serum or urine pregnancy test with a sensitivity of at least 25 mIU/mL within 10 to 14 days prior to starting lenalidomide. It is recommended to perform the pregnancy test as close to the date of randomization as possible in case there are drug shipment and treatment start date delays. A negative serum or urine pregnancy test must be repeated within 24 hours of starting lenalidomide and with each new cycle. Patients must also commit to continued abstinence from heterosexual intercourse or begin TWO acceptable methods of birth control, one highly effective method and one additional effective method AT THE SAME TIME, for 1) at least 28

days before starting study treatment; 2) while participating in the study; 3) during dose interruptions; and 4) for at least 90 days after the last dose of protocol treatment. Patients of childbearing potential with regular or no menstrual cycles must agree to have pregnancy tests weekly for the first 28 days of study participation and then every 28 days while on study, at study discontinuation, and at day 28 following discontinuation from the study. If menstrual cycles are irregular, the pregnancy testing must occur weekly for the first 28 days and then every 14 days while on study, at study discontinuation, and at days 14, and 28 following discontinuation from the study. Men must agree to use a latex condom during sexual contact with a partner of childbearing potential while participating in the study and for 90 days after the last dose of protocol treatment even if they have had a successful vasectomy. See [Appendix VI](#): Risks of Fetal Exposure, Pregnancy Testing Guidelines and Acceptable Birth Control Methods

Rev. Add3 5. Please refer to Section [6.3.2](#) for the PRO assessment schedule.

Rev. Add3 6. The Patient Medication Calendar must be completed for each cycle of treatment to record ixazomib/placebo and lenalidomide capsules taken. Please see [Appendix II](#): Patient Medication Calendar.

Rev. Add3 7. Serum and urine immunofixation and serum FLC only need to be repeated to confirm sCR or CR.

Rev. Add3 8. Within 8 weeks of pre-registration Step 0.

Rev. Add3 9. Follow-up post-treatment till progression. After progression, follow for survival for a maximum of 10 years. Every 3 months if patient is < 2 years from randomization, every 6 months if patient is 2-5 years from randomization, every 12 months if patient is 5 years or more from randomization. No specific requirements if patient is more than 10 years from randomization.

10. All specimens must be entered and tracked via the online ECOG-ACRIN Sample Tracking System (STS). See Section [10.3](#)

11. End of cycles 12, 24, 36 and 60 (\pm 6 weeks) only

12. End of cycles 12 and 24 (\pm 6 weeks) only

13. Institutions must upload immunofixation test results via Medidata Rave to determine eligibility status for Step 1 randomization.

14. Please refer to Section [8.2.8](#) and www.celgeneriskmanagement.com for information about the Revlimid REMS® program.

15. As clinically indicated.

Rev. Add3 16. Height is only required at baseline (prior to randomization) and does not need to be repeated.

8. Drug Formulation and Procurement

Investigator Brochure Availability

The current versions of the IBs for the agents will be accessible to site investigators and research staff through the PMB OAOP application. Access to OAOP requires the establishment of a CTEP IAM account and the maintenance of an “active” account status, a “current” password and active person registration status. Questions about IB access may be directed to the PMB IB Coordinator via email.

Useful Links and Contacts

- CTEP Forms, Templates, Documents: <http://ctep.cancer.gov/forms/>
- NCI CTEP Investigator Registration: [contact]
- PMB policies and guidelines:
http://ctep.cancer.gov/branches/pmb/agent_management.htm
- PMB Online Agent Order Processing (OAOP) application:
<https://ctepcore.nci.nih.gov/OAOP>
- CTEP Identity and Access Management (IAM) account:
<https://ctepcore.nci.nih.gov/iam/>
- CTEP IAM account help: [contact]
- IB Coordinator: [contact]
- PMB email: [contact]
- PMB phone and hours of service: [contact] Monday through Friday between 8:30 am and 4:30 pm (ET)

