6.1.1.4 Response Evaluation and Confirmation

In order to assess hematologic response categories of sCR, CR and VGPR, assessment of serum M-protein, serum immunoglobulin free light chain and urine M-protein will need to be performed as applicable. Confirmation of these results must be made by verification on two consecutive determinations.

A second confirmatory bone marrow is **not** required to confirm response in any case.

Radiographic studies are not required to satisfy these response requirements; however, if radiographic studies were performed there should be no evidence of progressive or new bone lesions.

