6.2.1.1 Sustained MRD Negative

MRD negativity in the marrow (NGF or NGS, or both) and by imaging as defined below, confirmed minimum of 1 year apart. Subsequent evaluations can be used to further specify the duration of negativity (e.g., MRD-negative at 5 years)

6.2.1.2	Flow MRD Negative Absence of phenotypically aberrant clonal plasma cells by NGF on bone marrow aspirates using the EuroFlow standard operation procedure for MRD detection in multiple myeloma (or validated equivalent method) with a minimum sensitivity of 1 in 10^5 nucleated cells or higher
6.2.1.3	Sequencing MRD Negative Absence of clonal plasma cells by NGS on bone marrow aspirates in which presence of a clone is defined as less than two identical sequencing reads obtained after DNA sequencing of bone marrow aspirates using the ClonoSEQ platform (or validated equivalent method) with a minimum sensitivity of 1 in 10^5 nucleated cells or higher
6.2.1.4	Imaging Plus MRD Negative MRD negativity as defined by NGF or NGS plus disappearance of every area of increased tracer uptake found at baseline or a preceding PET/CT or decrease to less than mediastinal blood pool SUV or decrease to less than that of surrounding normal tissue
6.2.2	Standard IMWG Response Category
6.2.2.1	Stringent Complete Response (sCR) CR as defined below plus all of the following: 
• Normal serum FLC ratio at two consecutive times and• Absence of clonal cells in bone marrow by immunohistochemistry or 2- to 4- color flow cytometry.^a• Presence/absence of clonal cells is based upon the κ/λ ratio. An abnormal κ/λ ratio by immunohistochemistry requires a minimum of 100 plasma cells for analysis. An abnormal ratio reflecting presence of an abnormal clone is κ/λ ratio of 4:1 or 1:2.
6.2.2.2	Complete Response (CR) Patients who have complete disappearance of an M-protein and no evidence of myeloma in the bone marrow are considered to have complete response. To be considered CR, patients must meet all of the following criteria: 
• Negative immunofixation on the serum and urine• Disappearance of any soft tissue plasmacytomas• $\leq 5\%$ plasma cells in bone marrow• If the only measurable disease is FLC, a normal FLC ratio of 0.26-1.65
6.2.2.3	Very Good Partial Response (VGPR) 
• Serum M-protein detectable by immunofixation but not quantifiable on electrophoresis AND

- Urine M-protein < 100 mg/24 hours

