9.2.1.2 Secondary Endpoints

- Progression-free survival defined as the time from randomization until the earlier of progression or death due to any cause, or censored at date of last disease evaluation (Note: Only deaths that occur within 3 months of the last disease evaluation are considered events.)
- Best response on treatment for eligible patients based on standard IMWG criteria as described in Section 6; Response rates for eligible patients including very good partial response (VGPR), complete response (CR) and stringent CR (sCR) at 12-, 24-, 36- and 60-cycles post-randomization
- Incidence of adverse events by worst grade and type for treated patients determined using CTCAE; Rates of worst grade 3 or higher non-hematologic toxicity and overall worst grade 3 or higher toxicity on treatment

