9.3.2 Secondary Clinical Analyses

Progression-Free Survival (PFS)

An important secondary aim is to evaluate whether a response-adapted strategy translates into superior progression-free survival for patients switching to more-intensive treatment. PFS will be estimated using the KM method and compared using the stratified log-rank test. Median PFS on the control arm is assumed to be 18 months based on results from recent clinical trials. Assuming exponential distribution of failures, this study is design to detect a 44% increase in median PFS to 26 months on the experimental arm. This corresponds to a treatment HR approximating 0.70 [monthly hazard rate 0.0385 versus 0.0267]. At 1-sided 2.5% type I error, there is approximately 90% power using a log-rank test to detect this HR given 510 patients uniformly accrued over 3.5y with full information of 319 PFS events at 4.5y (accrual end plus one year). The actual timing of this PFS analysis will depend on accrual. The analysis will not be done before one year after the last patient is randomized. No interim analyses for the PFS comparison will be conducted. The study team will also not consider or declare the experimental arm to be a success based on the PFS endpoint alone.

Response

Response will be tabulated by category. Response rates (sCR, CR, VGPR) will be compared using the chi-squared test for proportions. It is hypothesized that the ixazomib-lenalidomide arm will have higher response rates. Ineligible patients are excluded from the analysis and unevaluable patients are counted in the denominator. Sensitivity analyses will exclude unevaluable patients from the rate calculations. Given 255 patients per arm, there is over 90% to detect a difference of 15% in VGPR rates at 1-sided 2.5% significance assuming a 52.5% overall VGPR rate.

Toxicity

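### Once CR is confirmed, the schedule does not plainly require the immunofixation and FLC tests on which the 12-, 24-, 36- and 60-cycle CR and sCR rates depend

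*Combined protocol and SAP*

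**What the plan says.** **Endpoint.** Section 9.2.1.2 lists best response on treatment and then, after a semicolon, response rates including VGPR, "complete response (CR) and stringent CR (sCR) at 12-, 24-, 36- and 60-cycles post-randomization". Section 9.3.2 compares sCR, CR and VGPR rates by chi-squared test and adds: "Ineligible patients are excluded from the analysis and unevaluable patients are counted in the denominator". A sensitivity analysis drops the unevaluable patients.

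**Definitions.** CR (6.2.2.2) needs, among other things, "Negative immunofixation on the serum and urine". VGPR (6.2.2.3) is "Serum M-protein detectable by immunofixation but not quantifiable on electrophoresis", with a limit on urine M-protein. sCR adds a normal FLC ratio, and CR needs a normal ratio when FLC is the only measurable disease. On confirmation, section 6.1.1.4 says: "Confirmation of these results must be made by verification on two consecutive determinations".

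**Schedule.** Section 7.1 marks immunofixation and FLC in the end-of-cycle column subject to footnote 7: "Serum and urine immunofixation and serum FLC only need to be repeated to confirm sCR or CR". SPEP and UPEP are marked every cycle under footnote 3 ("Assessment is required if used to assess disease response"). Serum immunoglobulins are also marked every cycle. Marrow is due at "End of cycles 12, 24, 36 and 60", with a window of 6 weeks either side.

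**The concern.** The marrow is timed to the four landmarks, but the blood and urine tests that decide CR are not. Take a patient whose CR has been confirmed and whose M-protein later returns at a level visible only on immunofixation. By definition this patient is now VGPR. The per-cycle electrophoresis cannot show the change, and a marrow with few plasma cells does not settle it, because CR requires every criterion to be met. Footnote 7 names only confirmation of sCR or CR as a reason to repeat immunofixation. It does not mention the landmarks, and it does not mention VGPR, although VGPR is itself defined by an immunofixation result.

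The group concerned need not be small. Section 3.2.3 admits patients with residual disease by central MRD testing or by a monoclonal protein, so MRD-positive patients already in CR can be randomized. For them, a change in response category often means losing CR.

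At stake is whether landmark CR and sCR rates can be determined from the data that a compliant site would collect. A test not done at the time cannot be recovered at analysis.

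**Working it through.** **1. What a compliant site holds at cycle 24 for a patient with an earlier confirmed CR**

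| Needed to classify | Required at the landmark? |
|---|---|
| SPEP and 24-hour UPEP | Marked every cycle (footnote 3 condition) |
| Marrow | Yes (footnote 11) |
| Serum and urine immunofixation | Not plainly: CR is already confirmed |
| Serum FLC, for sCR or FLC-only disease | Not plainly: same footnote |

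A measurable spike, a marrow relapse or progression would be seen. An immunofixation-only or FLC-only loss of CR might not be.

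**2. The plan's own figure.** Section 9.3.2 gives power above 90% for a 15-point VGPR difference, 255 per arm, one-sided 2.5%, overall rate 52.5% (so 45% against 60%).

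z = [0.15 − 1.96·√(2·0.525·0.475/255)] / √((0.45·0.55 + 0.60·0.40)/255) = (0.15 − 0.0867)/0.0437 = 1.45, so power is 92.6% (91.3% with continuity correction). The figure reproduces. It concerns VGPR; no power is stated for CR.

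**3. Direction of the effect.** Let e be the share of an arm ever in CR by the landmark and l the fraction of those with an undetected loss (C control, A ixazomib).

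- CR carried forward: difference = eA − eC.
- True current status: difference = eA(1 − lA) − eC(1 − lC).
- Carried minus true = eA·lA − eC·lC.

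Carrying forward therefore shrinks the difference only if control loses more CRs in absolute terms. The inputs below are assumptions; the documents give none. With eC = 20% and eA = 30%, the carried difference is always 10.0 points (power 74% at 255 per arm).

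| Loss C / A | True rates | True difference | Power | Effect of carrying forward |
|---|---|---|---|---|
| 10% / 10% | 18% v 27% | 9.0 | 68% | widens |
| 20% / 20% | 16% v 24% | 8.0 | 62% | widens |
| 20% / 15% | 16% v 25.5% | 9.5 | 76% | widens |
| 20% / 10% | 16% v 27% | 11.0 | 86% | shrinks |
| 30% / 10% | 14% v 27% | 13.0 | 96% | shrinks |

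Suppose instead that 10 to 30% of CR patients in each arm are untested and count as non-responders. Reported rates then fall to 18–14% and 27–21%, and the difference to 9.0–7.0 points. CR is understated.

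**4. Possible size, with time in the model.** States: CR, CR lost without progression, progression. With CR share c at the start, yearly loss rate h, and g = ln 2 / (median years from loss to progression):

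- true CR at t = c·exp(−ht)
- carried-forward excess = c·h/(g − h)·[exp(−ht) − exp(−gt)]
- t = 24·28/365.25 = 1.84 years

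Assume c = 40% in both arms, h = 0.1 to 0.3 on control, 0.7 times that on ixazomib, and a median of 0.5 to 1.25 years from loss to progression. The excess is 2.3 to 10.2 points on control and 1.7 to 7.8 on ixazomib. These are upper bounds, because the model hides every lost CR until progression. Serum progression needs a rise of at least 0.5 g/dL (6.2.2.4), so a smaller measurable spike would already end CR visibly.

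Arm difference with control c = 40% and h = 0.2, treating any extra ixazomib CRs as present from the start:

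| Ixazomib c | Loss-rate ratio | True difference | Reported if carried forward |
|---|---|---|---|
| 40% | 0.70 | 3.2 | 1.3–2.2 |
| 55% | 0.70 | 14.8 | 15.0 |
| 50% | 0.85 | 8.9 | 9.3–9.6 |
| 50% | 1.00 | 6.9 | 8.0–8.8 |

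The first row needs no additional CRs on ixazomib. Section 9.3.2 hypothesizes higher response rates there.

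**The case against.** **Footnote 7 can be read more generously.** Immunofixation is marked in the end-of-cycle column, so a site might repeat it whenever CR is claimed, including at a landmark. That reading is possible. But the footnote limits when repetition is needed, and CR that has met the two-determination rule is already confirmed. Sites could reasonably differ.

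**Landmark rates might mean best response to date.** Section 9.2.1.2 does not say. If so, later loss of CR is irrelevant. Against this, best response is listed as its own item and the marrow is timed to the same four cycles, which makes current status the more natural reading. The text should settle it.

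**A reader might infer that a patient who has lost CR is still counted as CR, which inflates the rates and dilutes the arm difference.** The documents do not support this. No section carries an earlier CR forward. Under section 9.3.2 an untested patient could be unevaluable and count against CR. Even with carrying forward, the arm difference can widen.

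**A reader might also infer that any loss of CR short of progression is invisible.** It is not: electrophoresis, immunoglobulins and the landmark marrow leave only immunofixation-only or FLC-only loss hidden.

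**The reach is limited.** This stands. The only powered response comparison is VGPR. If that means VGPR or better, as section 9.2.1.3 words it for duration of response, a patient who drops from CR to VGPR does not change the rate.

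**Conclusion.** The gap is real and lies in an operative rule. A site that follows the calendar need not hold the result that separates CR from VGPR, or the FLC that sCR requires, at the landmarks where those rates are secondary endpoints. Landmark CR and sCR rates would rest on local testing habits and an unstated convention for untested patients.

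Direction and size cannot be fixed from the documents, which give no CR rate, CR-loss rate or time from CR loss to progression. The overstatement of roughly 2 to 10 points on control at 24 cycles is an upper bound that depends on the assumed inputs and on carrying CR forward. The opposite convention gives an understatement. No claim that the arm difference is diluted should be made.

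OS, best response on treatment and a VGPR-or-better rate are unaffected by immunofixation-only loss. Such a loss is not progression under section 6.2.2.4 either. However, footnote 7 also limits FLC, which that section uses for progression in patients without measurable M-protein. That is a further reason to include FLC in the fix; its effect is not measured here.

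This is worth changing because the cost is small and the missing results cannot be recovered later.

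**What to change.** - **Section 7.1, footnote 7:** require serum and urine immunofixation and serum FLC at the end of cycles 12, 24, 36 and 60, in the same window as the marrow, and also whenever sCR, CR or VGPR is to be confirmed.
- **Section 9.2.1.2:** state that landmark categories are current status, based on tests from that window.
- **Section 9.2.1.2 or 9.3.2:** state how a patient without immunofixation or FLC in the window is classified, and apply the same rule in both arms.

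Cost: at most four extra assay sets per patient, at visits where SPEP and UPEP are already scheduled. No additional visit, marrow or patients are needed.
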